2.4.4 Poolability Analysis

The distribution in AE free-rates across centers will be examined. The significance of differences in rates between centers will be initially tested using a Kruskal-Wallis test statistic, with an associated p-value of 0.15 or less considered evidence of center differences.

A Cochran-Mantel-Haenszel test with continuity adjustment will be used to assess the poolability of data collected across the different centers. If evidence is found of center differences, then the reasons for the differences will be explored using Cox and logistic regression methods to determine if any baseline subject risk factors are explanatory.

3. PROTOCOL REQUIREMENTS

3.1 SUBJECT POPULATION

The investigator is responsible for screening all potential subjects and selecting those who are appropriate for registry inclusion. Those selected for participation should be from the investigator's general patient population according to the indications below. Additionally, potential subjects will be evaluated against the inclusion and exclusion criteria described in Sections 3.1.3 and 3.1.4.

3.1.1 Indications

The Protego lead is a 7.8 French (8 F introducer) transvenous, steroid-eluting, bipolar, DF4 compatible ICD lead intended for permanent implantation in the right ventricle to provide pacing/sensing in the right ventricle and defibrillation/cardioversion shocks to the heart. For this registry, the Protego lead is utilized in conjunction with any market-released BIOTRONIK Icesto or future US market released ICD/CRT-D device with a DF4 header.

3.1.2 Contraindications

Transvenous endocardial leads are contraindicated in the presence of severe tricuspid valvular disease and in patients with a mechanical tricuspid valve. The Protego DF4 lead is additionally contraindicated for patients who cannot tolerate a single systemic dose of dexamethasone acetate (DXA) of up to 1.3 mg for active fixation leads or 1.0 mg for passive fixation leads.

3.1.3 Inclusion Criteria

To support the objectives of this investigation, patients are required to meet the following inclusion criteria prior to enrollment:

- Implanted within the last 30 days or candidate for implantation of a BIOTRONIK ICD or CRT-D DF4 compatible system along with the Protego DF4 lead
- Meets ICD or CRT-D system implant recommendations as defined in guidelines published by relevant professional societies
- Able to understand the nature of the registry and provide informed consent
- Available for follow-up visits on a regular basis at the investigational site for the expected 5 years of follow-up
- Age greater than or equal to 18 years

3.1.4 Exclusion Criteria

To support the objectives of this investigation, the exclusion criteria at the time of patient enrollment include the following requirements:

- Enrolled in any investigational cardiac device trial
- Planned cardiac surgical procedures or interventional measures within the next 6 months
- Expected to receive heart transplantation or ventricular assist device within 1 year
- Life expectancy of less than 1 year
- Presence of another life-threatening, underlying illness separate from their cardiac disorder
- Patients reporting pregnancy at the time of enrollment

3.2 REGISTRY PROCEDURES

Patients will be enrolled \pm 30 days from implant of a BIOTRONIK DF4 compatible ICD or CRT-D device and Protego lead. BIOTRONIK Home Monitoring® should be activated in subjects who have a Home Monitoring® system. Home Monitoring® data can be utilized to assist in triage and diagnosis of lead-related adverse events between scheduled follow-ups. Subjects with a Home Monitoring® system will be seen for a routine in-office follow-up at least every 12 months and have the option to be followed by Home Monitoring® between routine in-office follow-ups at the intervening 6 month intervals. Subjects without a Home Monitoring® system will be seen for a routine in-office follow-up at least every 6 months.

Registry Procedure Visits:

- Enrollment
- Implant (collected retrospectively if before enrollment)
- Routine follow-up evaluations at 3 months post-implant and every 6 months post-implant for 5 years
- Interim evaluations for Protego lead-related events or system revisions

Table 4 summarizes the visit assessment schedule.

Table 4: Registry Visit Assessment Schedule

	Enrollment	Implant ¹	Routine Follow-up 3 Months and 6-60 Months (every 6 months ± 1 month) ²	Interim Evaluation (if applicable)
Informed Consent (enrollment)	X			
Demographics and Medical History	X			
Collect Implant Information	X ³	X ³		X
Device Evaluation		X	X	X
Adverse Event Assessment		X	X	X
Complete eCRF	X	X	X	X

¹Implant must be completed within 30 days of or no more than 30 days prior to enrollment/informed consent.

²Subjects using Home Monitoring® will be seen for a routine in-office follow-up at least every 12 months and may be followed by Home Monitoring® between routine in-office follow-ups at the intervening 6 month intervals. Subjects not using Home Monitoring® will be seen for a routine in-office follow-up at least every 6 months. If a registry visit is conducted via Home Monitoring® the site is required to call the subject on the date of the Home Monitoring® data collection and document the Investigators assessment of possible adverse events since the last registry visit.

³If implant was completed prior to enrollment, implant data is collected retrospectively at the enrollment visit. If the subject was enrolled prior to implant, implant data will be collected and entered at the time of the implant procedure.

3.2.1 Registry Pre-Screening

Prior to enrollment, the patient's medical history must be reviewed in order to ensure they are an appropriate candidate for the registry. In addition, all patients must satisfy the registry inclusion and exclusion criteria prior to enrollment, including being a candidate for or having been implanted with a BIOTRONIK Protego lead and DF4 compatible ICD or CRT-D within the last 30 days.

3.2.2 Enrollment Visit

If the patient has been determined to be eligible for the registry, informed consent must be obtained from the patient prior to initiating any registry related procedures. The consent process, including discussion of the registry, will be documented in the patient's medical record. A patient is considered enrolled in the registry upon signing the Informed Consent Form and undergoing an attempt to implant the Protego DF4 lead. If a patient is consented and undergoes enrollment procedures prior to implant, they are considered 'provisionally enrolled' until they are successfully implanted, at which time they are considered fully enrolled. The visit at which informed consent is obtained is the enrollment visit and occurs ± 30 days from the date of implant. If implant occurs prior to enrollment, the date of implant and system information must be available for the patient to be enrolled. Patient demographics are to be obtained at the enrollment visit; however,

height and weight may be historical if this information is not available, with proper source documentation.

The following data collection and reporting procedures are performed at the enrollment visit:

- Obtain Informed Consent
- Collect subject demographics (gender, height, weight, etc.)
- Medical history of subject, including device implant indications
- Complete all required eCRFs

3.2.3 Protego Implant

Implant will be completed \pm 30 days from the enrollment visit. Implant details and device data will be collected retrospectively if implant occurred prior to enrollment.

The following data collection and reporting procedures are performed at implant:

- Collect implant information
 - o Date of implant
 - o Implant approach/method, and venous access
 - o Implant success
 - o If DFT testing was completed during implant, shock energy and impedance used during test
- Collect information on implanted system (pulse generator and leads manufacturer/model, serial numbers, etc.).
- Record electrical parameters of the implanted leads. Perform all pacing threshold measurements at 0.4 ms or 0.5 ms pulse width.
- Record any lead-related, pulse generator-related and procedure-related adverse events during implant and complete an Adverse Event eCRF. Protego lead related adverse events should be reported even if the implant attempt is unsuccessful.
- Program parameters to best suit the needs of the subject.
- Complete all required eCRFs.

Patients that are provisionally enrolled, but never successfully implanted with the Protego lead, will be considered screen failures. If they undergo an implant attempt, but are not successfully implanted due to a Protego lead related adverse event (such as

cardiac perforation caused by the Protego lead) they will also be included in the intention-to-treat (ITT) population.

3.2.4 Routine Follow-ups

Three and six months (± 30 days) after successful implant and every six months (± 30 days) thereafter, subjects will undergo an assessment of their implanted system. Subjects with Home Monitoring® capabilities will be seen for a routine in-office follow-up at least once every 12 months and have the option to substitute a Home Monitoring® evaluation for every other in-office follow-up to result in the six month follow-up schedule. Additionally, each Home Monitoring® follow-up will be accompanied by an assessment via telephone call within 7 days, documenting clinical signs and symptoms. Subjects not using Home Monitoring® will be seen for a routine in-office follow-up at least once every six months.

Each site Principal Investigator (PI) will be trained to identify and schedule follow-ups to meet the required visit expectation. Additionally, the EDC will provide assistance in identifying properly scheduled follow-ups according to this protocol.

The following study procedures are performed at routine in-office follow-ups:

- Interrogate and print initial programmed parameters and view stored diagnostic data.
- Record and print electrical parameters of the implanted leads. Perform all pacing threshold measurements at 0.4 ms or 0.5 ms pulse width.
- Evaluate device diagnostics, electrical parameters and programmed parameters to ensure the device is correctly pacing, sensing, and providing appropriate therapy.
- Record and print cumulative episode counters.
- Determine if there have been any adverse events (as defined in Section 10). If any are recorded, complete an Adverse Event eCRF.
- Interrogate and print the final programmed parameters.
- Complete all appropriate eCRFs.

The following study procedures are performed for a Home Monitoring® evaluation:

- Collect programmed parameters and view stored diagnostic data.
- Record electrical parameters of the implanted leads.
- Evaluate device diagnostics, electrical parameters and programmed parameters to ensure the device is correctly pacing, sensing, and providing appropriate therapy.
- Record cumulative episode counters.

-
- Perform phone interview within 7 days of Home Monitoring® report.
 - Determine if there have been any adverse events (as defined in Section 10). If any are recorded, complete an Adverse Event eCRF.
 - Complete all appropriate eCRFs.

3.2.4.1 Device Programming

If Home Monitoring® evaluations will be used for routine follow-up visits, atrial and ventricular capture control should be programmed to “ON” or “ATM,” and Home Monitoring® activated. If atrial and ventricular capture control is not programmed “ON”/“ATM” or goes off automatically due to AF, high intrinsic rate, or other reason, the investigator will provide reasons in the EDC system.

3.2.5 **Unscheduled Interim Follow-ups**

Unscheduled interim follow-ups may occur anytime during the registry. Data collection is only required when a subject is seen for Protego lead-related reasons or due to a protocol defined adverse event. Other hospital or clinic visits that are unrelated to the device are not required to be entered into the EDC system.

3.2.5.1 Protego Related Interim Follow-ups

For unscheduled interim in-office follow-ups related to the Protego lead (but not including a system revision), the data collection and reporting requirements are the same as those required for routine follow-ups (Section 3.2.4).

3.2.5.2 System Revisions

For interim evaluations that involve a system revision (even if the Protego lead is not directly affected), the following are required:

- Collect implant information
 - o Date of revision
 - o Implant approach/method, and venous access
 - o Implant location of pulse generator and implanted leads
- Record extraction experience (if applicable).
- Collect information on newly implanted system (pulse generator and leads manufacturer/model, serial numbers, etc.).
- Record electrical parameters of the implanted leads. Perform all pacing threshold measurements at 0.4 ms or 0.5 ms pulse width.

-
- Record any lead-related, pulse generator-related and procedure-related adverse events during implant and complete the Adverse Event eCRF.
 - Set programming parameters to best suit the needs of the subject.
 - Complete System Revision and Out of Service (OOS) eCRF, as applicable.

If the Protego lead is replaced with another Protego lead, the subject will continue participation in the registry based on the original implant date and visit schedule. If the Protego lead is explanted and the subject does not receive a new Protego lead, the subject will be withdrawn from the registry. See Section 3.3.3 for details on withdrawals due to lead or pulse generator extraction.

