2.3 SAMPLE SIZE ANALYSIS

The estimated sample sizes required to evaluate primary endpoints 1 and 2 are based on a superiority comparison of the overall Protego DF4 lead AE free-rate to 92.5% at 5 years, and a non-powered, superiority comparison for those individual lead-related AEs to 1% at 5 years. The sample size for primary safety endpoint 1 was calculated based on the following assumptions:

Assumptions for primary safety endpoint 1

- Study Design: nonrandomized registry
- Test basis: exact binomial test
- Type I error (alpha): 0.025 (one-sided for superiority)
- Statistical power: 80%
- Estimated AE-Free Rate at 5 years: 95.0% for Protego Leads
- Performance goal for AE-Free Rate at 5 years: 92.5%

For primary safety endpoint 1, a total of 750 evaluable Protego leads would be required to demonstrate superiority to an AE free-rate of 92.5% (see Table 3). Assuming a 10% loss to follow-up rate per year over 5 years of follow-up (average of 8.2% of original population per year), a total of 1271 ($=750/0.9^5$) subjects with an ICD lead would be required to be enrolled to evaluate primary safety endpoint 1.

Assumptions for primary safety endpoint 2

- Estimated individual AE rate at 5 years: 0.4%
- Allowable two-sided, upper 95% confidence bound: 1%

For primary safety endpoint 2, a total of 1000 evaluable subjects with Protego DF4 leads would be required to demonstrate a two-sided, upper 95% confidence bound of 1%, assuming an expected individual AE rate of 0.4% (see Table 3). Assuming a 10% loss to follow-up rate per year over 5 years of follow-up (average of 8.2% of original population per year), a total of 1694 ($=1000/0.9^5$) subjects would be required for evaluation of primary safety endpoint 2.

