2.4.3 Missing Data

All possible steps will be taken to minimize missing data in the registry. This includes but is not limited to monitoring of registry forms for completeness and supporting efforts to track and maintain contact with registry subjects during the follow-up period.

The reasons for any missing data in the registry will be documented. BIOTRONIK will examine both missing-data patterns, which describe which values are observed and which are missing, and the missing-data mechanisms, which concerns the relationship between missingness and the values of variables in the registry data set².

For evaluation of the long-term primary registry endpoints (safety endpoints 1 and 2), only subjects who achieve 5 years of follow-up or have experienced an adverse event prior to 5 years will be included in the final evaluation of the associated hypotheses. The secondary endpoint of other AEs at 5 years, excluded from the primary safety analyses, will be analyzed in similar manner. There will be no imputation for these missing adverse event outcomes.

For purposes of Kaplan-Meier survival analyses, described in Section 2.4.2, all AE data on enrolled subjects will be included with follow-up times censored at the time of withdrawal or last completed follow-up visit representing the time of the last known AE status.

² R.J.A. Little and D.B. Rubin, 2002, *Statistical Analysis with Missing Data*, 2nd edition, Wiley and Sons

Secondary endpoints, which include successful sensing and pacing, pacing thresholds, sensing and impedance measurements will be analyzed in two ways. First, all available results will be summarized by scheduled visit through the 5 years of registry follow-up. Secondly, a last value carried forward (LVCF) will be used to estimate the values at the final 5-year follow-up evaluation for subjects who withdraw prior to 5 years.

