3.3.3 Protego Lead or Pulse Generator Extraction

Any subject who has the Protego lead explanted or capped, and is not implanted with another Protego lead, will be withdrawn from the registry. Additionally, any subject who has their BIOTRONIK pulse generator explanted and replaced with a non-BIOTRONIK device will also be withdrawn from the registry (even if the Protego lead remains). Only complete a registry exit eCRF after documentation of the system revision procedure (see Section 3.2.5.2) is available. For example, if the Protego lead and pulse generator are explanted due to infection, the subject should not be exited until a non-registry lead/system is implanted or documentation is available stating that the subject will not be re-implanted with a registry qualifying lead/system. Report the exit on the Registry Exit eCRF and any adverse events resulting from the explant procedure.

Whenever possible, devices that are explanted must be returned to BIOTRONIK for analysis.

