10.2 ENDPOINT ANALYSIS

All protocol defined adverse events included in the primary and secondary endpoint analysis will be adjudicated by the Clinical Events Committee (CEC) (see Section 2.1). The CEC will have the responsibility to adjudicate the classification and category of each reported adverse event as implant procedure, implanted pulse generator, lead, or non-procedure non-system related. For each adverse event, the CEC will indicate whether the adverse event relatedness to the Protego lead is: not related, related, possibly related, or unknown.

In evaluation of the two primary endpoints for the post-approval registry, the estimates of AE rates will be based on the number of subjects with at least one "related" AE as a proportion of total subjects. Subjects with a final adjudicated related AE classification of "possibly related", "not related" or "unknown" will not have that individual event contribute to or be included in the evaluation of primary safety endpoints. The same rules will be used for purposes of Kaplan-Meier survival analyses, described in Section 2.4.2.

Secondary endpoint 3, which includes AEs that were excluded from primary safety endpoint 1 through 5 years post-implant, will also be summarized as AE rates along with their associated, exact 95% confidence intervals.

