APPENDIX A: DEFINITION OF TERMS

AE (Adverse Event) – An unwanted affect detected in participants either implant procedure-related, pulse generator-related, lead-related, or other. The term is used whether or not the effect can be attributed to the leads in the study. For the purposes of this study, the CEC will indicate whether the adverse event relatedness to the Protego lead is: not related, related, possibly related, or unknown.

ACC/AHA – American College of Cardiology/American Heart Association

Cardiac Perforation – Penetration of the lead tip through the myocardium (including microperforation), either clinically suspected or confirmed by chest x-ray, fluoroscopy, echocardiogram, intracardiac electrogram and/or visually.

CEC – Clinical Events Committee

Clinical Failure – Inability of the lead to correctly sense or pace in the heart, not attributable to a mechanical malfunction of the lead or pulse generator that remains unresolved despite reprogramming and/or repositioning.

CFR – Code of Federal Regulations

Conductor Fracture – See Lead Fracture

Confirmed Failure – A lead having clinically relevant characteristics that are outside the performance limits established by BIOTRONIK while implanted and in service, as confirmed by analysis, except for changes in characteristics that are due to induced malfunctions. Lead damage caused during or after explant is not considered a failure.

Chronic Threshold – Chronic threshold is defined as the pacing threshold determined at the subject's 3 month follow-up visit.

eCRF – Electronic Case Report Form

EDC – Electronic Data Capture system

Exit Block – The failure of an intact pacing system to capture the heart because the stimulation threshold exceeds the output of the pacemaker.

Explantation – Surgical removal of a lead during the acute implant stage, whereby the lead has not been chronically implanted and can be easily removed by simple traction.

Extracardiac Stimulation – Clinical observation of inadvertent nerve/muscle stimulation other than cardiac muscle, such as the diaphragm or pectoral muscles.

Extraction of a Lead – Surgical removal of a chronically implanted lead.

Failure to Capture or Loss of Capture – Intermittent or complete failure to achieve cardiac stimulation at programmed output delivered outside of the cardiac refractory period.

High Pacing Threshold – One of the following definitions must be met:

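### Readings from a replacement Protego lead are tabulated at the removed lead's time since implant, so some 60-month values in secondary endpoints 1 and 2 come from younger leads

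*Combined protocol and SAP*

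**What the plan says.** Section 3.2.5.2 covers a like-for-like replacement: "If the Protego lead is replaced with another Protego lead, the subject will continue participation in the registry based on the original implant date", and the original visit schedule is kept as well. With any other outcome the subject leaves: "If the Protego lead is explanted and the subject does not receive a new Protego lead, the subject will be withdrawn from the registry". Section 3.3.3 repeats this and adds capped leads: "Any subject who has the Protego lead explanted or capped, and is not implanted with another Protego lead, will be withdrawn from the registry".

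For secondary endpoints 1 and 2 (pacing threshold, sensing, pacing impedance and shock impedance through 5 years), section 2.4.3 gives two analyses. In the first, "all available results will be summarized by scheduled visit through the 5 years of registry follow-up". In the second, the last value is carried forward to year 5 for subjects who withdraw early. Section 2.4.1 lists minimums and maximums among the reported statistics.

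The primary endpoints are per subject. In section 10.2, "the estimates of AE rates will be based on the number of subjects with at least one" event adjudicated as related. Section 10.3.1 counts a Protego lead-related event resolved by surgical replacement as a primary event. The binomial test in section 2.4.3 uses subjects who reach 5 years or have an earlier event. Kaplan-Meier time is censored only at withdrawal or the last completed visit.

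Appendix A ties the reference for a raised pacing threshold to the subject: "Chronic threshold is defined as the pacing threshold determined at the subject's 3 month follow-up visit".

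**The concern.** The registry exists to describe how a Protego lead behaves over 5 years. A table headed month 60 will be read as the state of leads that have been in place for 60 months. Under the stated rules it also contains newer leads, and these enter in place of the leads removed, some of which will have been removed because their readings were abnormal. Late deterioration shows in the extremes of the distribution, and the extremes are what this substitution affects most.

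The rules also treat the same removal in two ways. If the successor is a Protego lead, its readings become the later values. If it is not, the subject is withdrawn and the old lead's last reading is carried to year 5. The recorded 5-year value then depends on which replacement was chosen.

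**Working it through.** **The plan's own figures.** Section 2.3 asks for 750 evaluable for endpoint 1 ("a total of 750 evaluable Protego leads would be required") and 1000 evaluable subjects for endpoint 2.

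- Endpoint 1, exact binomial test, goal 92.5%, true rate 95.0%, one-sided alpha 0.025: at n = 750 success needs at least 708 event-free (at most 42 events). Actual alpha is 0.0247 and power 80.1%.
- Attrition: 750/0.9^5 = 1270.1, giving 1271; 1000/0.9^5 = 1693.5, giving 1694.
- Endpoint 2: 4 events in 1000 has an exact upper 95% bound of 1.021%, which is 1% only after rounding.

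Section 2.3 uses leads as the unit in one place and subjects in the other; section 10.2 settles the unit as the subject.

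**Secondary endpoints 1 and 2.** If the lead is replaced r months after first implant, the lead read at the 60-month visit is 60 − r months old. For r = 54 that is 60 − 54 = 6 months; for r = 1 it is 59 months. Only late replacements are badly mislabelled.

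The same removal at month 54, followed through the rules:

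| Successor | Registry status | Year-5 value |
|---|---|---|
| Protego | Continues on the original clock (3.2.5.2) | New lead's reading, at age 6 months |
| Not Protego | Withdrawn (3.2.5.2, 3.3.3) | Old lead's last reading, in the carried-forward analysis |

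If a fraction f of the year-5 values comes from replacement leads, and these differ on average by d from the removed leads' last readings, the mean of the carried-forward analysis shifts by f × d. That is small when f is small. A maximum or minimum has no such protection, because one lead can set it. The documents do not give f.

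**Primary endpoint 1.** Two groups must be kept apart.

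- Replaced for a related primary event: already counted as a failure (10.2, 10.3.1). Later time on the new lead cannot undo that.
- Replaced for another reason: procedural lead damage (10.1.1, assigned to secondary endpoint 3 by 10.3.2), dislodgement or capture problems within the 30-day exclusion (10.3.1), or an event not adjudicated as related (10.2). Such a subject can reach month 60 and count as event-free.

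To size the second group, assume that 0.5% to 5% of 1000 evaluable subjects belong to it, with 50 events overall (95.0% event-free). Remove them as non-evaluable and recompute the exact lower 95% bound:

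| Removed | Event-free rate | Lower bound | Most events that still pass |
|---|---|---|---|
| 0 | 950/1000 = 95.00% | 93.46% | 58 |
| 5 | 945/995 = 94.97% | 93.43% | 58 |
| 10 | 940/990 = 94.95% | 93.40% | 57 |
| 20 | 930/980 = 94.90% | 93.33% | 57 |
| 30 | 920/970 = 94.85% | 93.26% | 56 |
| 50 | 900/950 = 94.74% | 93.12% | 55 |

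With 750 evaluable and 38 events, removing 5% (38 subjects) moves the lower bound from 93.11% to 92.75%. Every bound stays above 92.5%.

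**Primary endpoint 2.** A subject whose lead was replaced for one event type still accrues time free of the other types on the new lead. Removing up to 50 of 1000 subjects moves the upper bound from 0.874% to 0.920% for 3 events (still below 1%) and from 1.021% to 1.075% for 4 events (above 1% either way).

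**Pacing-threshold reference.** At follow-up the definition needs both a doubling from the 3-month value and a reading above 3.5 V (10.1.3, Appendix A). The reference matters only if it exceeds 3.5/2 = 1.75 V. Against the GALAXY mean of 0.63 V with SD 0.33 V (section 1.3.1), that is (1.75 − 0.63)/0.33 = 3.4 SD above the mean. The GALAXY figure is not specific to month 3, so this is only a guide.

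**The case against.** The rule in section 3.2.5.2 governs participation and visits. Keeping a subject in follow-up after a like-for-like replacement fits a per-subject, intention-to-treat design and captures further Protego events. The plan is not wholly blind to replacement either: section 10.3.1 restarts the 30-day exclusion after a lead revision. A lead replaced for abnormal readings and adjudicated related is captured in the primary endpoints, and readings are required at lead-related interim visits. Secondary endpoints 1 and 2 carry no hypothesis test. Ending the old lead's series at removal also takes the failed lead out of the month-60 column, so that step alone does not restore the abnormal tail.

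Most of this stands. It supports keeping the visit rule and the per-subject test, and it is why the removed lead's last reading must be shown and carried forward. It does not answer the labelling problem: no rule keeps a 6-month-old lead's reading out of the 60-month summary.

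Two stronger readings are tempting. A reader might infer that failed leads are turned into 5-year successes in endpoint 1. The documents do not support that, because replacement for a related event outside the 30-day exclusions is itself the failure. A reader might also take the GALAXY figure of 60 of 1,999 subjects (3.0%) as a replacement rate. It counts subjects with any primary or secondary lead-related event, not replacements, and still less replacements with the same type of lead.

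**Conclusion.** The concern holds for secondary endpoints 1 and 2: following the stated rules, some values reported at 60 months come from leads younger than 60 months, and the minimums and maximums are the statistics most exposed. How many is unknown, because no replacement rate is given; it is probably small.

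For the primary endpoints the point is minor. It is confined to replacements for non-endpoint reasons and, in endpoint 2, to the event types other than the one that led to replacement. Over the assumed 0.5% to 5%, the endpoint 1 rate moves by 0.03 to 0.26 percentage points and its lower bound by 0.03 to 0.34. No pass or fail changes at the planning values; only a result at the limit could (55 to 58 allowable events across the range, against 58 with none removed). The pacing-threshold reference is a real inconsistency that will rarely matter.

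**What to change.** Keep the visit schedule and the per-subject primary test. Then:

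- In secondary endpoints 1 and 2, end the original lead's series at removal. Show its last reading before removal, and use that reading in the carried-forward analysis whichever lead follows.
- Tabulate replacement-lead readings separately, by time since that lead's own implant.
- Add a lead-level Kaplan-Meier sensitivity analysis that censors at replacement for a non-endpoint reason.
- Reconcile the subject-based 3-month threshold reference in section 10.1.3 and Appendix A with the possibility that the lead has changed.
- State in section 5.2 which lead's implant date sets the visit schedule, in line with section 3.2.5.2.

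No new data are needed: revision dates, models and serial numbers are already collected (sections 2.1.4 and 3.2.5.2). The cost is one extra table, one sensitivity analysis and slightly fewer readings at late visits. Dropping these subjects from the binomial test is not recommended; it would discard known 5-year outcomes from a design that already allows for 41% attrition.
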